The hamstring-to-quadriceps (H:Q) ratio is an important indicator of knee joint stability, reflecting the balance between knee flexors and extensors. In healthy individuals, a conventional H:Q ratio of about 0.5–0.6 is typical, whereas elite athletes often display higher ratios due to sport-specific adaptations and targeted strength training (**Çelebi et al., 2018**). Sports involving explosive actions, rapid decelerations, and frequent directional changes place high demands on both muscle groups, making balanced strength essential for performance and injury prevention. Regular monitoring and tailored conditioning programs are therefore recommended to enhance performance and reduce injury risks (**Baroni et al., 2020**).

One critical aspect of lower limb strength balance in football players is the (H:Q) ratio, which reflects the relationship between the knee flexor and extensor muscles. A low H:Q ratio, where quadriceps strength disproportionately exceeds that of the hamstrings, has been strongly associated with a higher risk of hamstring strains and non-contact anterior cruciate ligament (ACL) injuries due to reduced dynamic knee joint stability during high-speed movements (**Grygorowicz et al., 2017**).

Statement of problem:

This study will try to answer the following question:

Will adding mini-squat exercises at different angles (30°, 45°, and 60°) to leg press exercise influence quadriceps and hamstring strength and H:Q angle in football players?

Purposes of the study:

The purposes of this study are to

1. To investigate the difference between adding knee flexion mini-squat exercise at different angles (30° , 45° , and 60°) to leg press exercise on quadriceps strength in football players.
2. To investigate the difference between adding knee flexion mini-squat exercise at different angles (30° , 45° , and 60°) to leg press exercise on hamstrings strength in football players.
3. To investigate the difference between adding knee flexion mini-squat exercise at different angles (30° , 45° , and 60°) to leg press exercise on the hamstring-to-quadriceps (H:Q) ratio in football players.

Significance of the study:

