Recent studies have highlighted the importance of exercise selection and angle specificity in resistance training, showing that different knee angles result in varied activation patterns in the quadriceps and hamstrings. However, current literature offers limited insight into the effects of integrating mini squat exercises with leg press training on injury prevention and functional outcomes in athletic populations. In particular, there is a lack of literature on how such a combined leg press and mini squat exercise at different angles influences the H:Q ratio, lower limb neuromuscular control, and performance in young male football players. Therefore, the present study aims to examine whether incorporating mini squats performed at varying knee flexion angles into a leg press training program can improve muscle balance and lower limb strength in football players. The findings may provide valuable guidance for physiotherapists, coaches, and sports scientists in developing evidence-based, angle-specific exercise protocols tailored to the functional demands of athletes. (**Watanabe et al., 2020**).

Delimitation:

This study will be delimited to the following:

1. Male football players aged between 18–30 years (**Scoz et al., 2021**).
2. Body Mass Index (BMI) between 18.5 and 24.9 kg/m² (**Walsh et al., 2018 & Sattar & Lean, 2009**).
3. Participants will receive 18 training sessions, conducted three days per week, over six successive weeks

Basic assumptions:

1. Participants understood and followed the given instructions during assessment and treatment procedures.
2. Participants did not receive any additional medical or physical therapy treatment during the study period.

Hypotheses will be:

1. There is no statistically significant difference between adding 30°, 45°, and 60° knee flexion mini-squat exercises to leg press exercise and leg press exercise alone on quadriceps strength in football players.
2. There is no statistically significant difference between adding 30°, 45°, and 60° knee flexion mini-squat exercises to leg press exercise and leg press exercise alone on hamstrings strength in football players.
3. There is no statistically significant difference between adding 30°, 45°, and 60° knee flexion mini-squat exercises to leg press exercise and leg press exercise alone on the hamstrings-to-quadriceps H:Q ratio in football players.

Definitions of terms

Hamstring-to-quadriceps ratio H:Q ratio:

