SUBJECTS, MATERIALS AND METHODS

The current study aims to investigate whether incorporating mini squat exercises at different knee flexion angles into a leg press training program enhances hamstring- quadriceps ratio H:Q ratio in football players.

Design of the study:

This study will follow a randomized controlled trial (RCT) design.

Study setting

The study will be conducted at the outpatient physical therapy clinic of Jazan University Hospital, kingdom of Saudi Arbia.

Sample size:

The sample size for this study was determined using G*Power version 3.1.9 (Heinrich-Heine-University, Düsseldorf, Germany). An a priori power analysis was conducted for a repeated measures MANOVA with between-subject factors, setting the alpha level (α) at 0.05, desired power ($1 - \beta$) at 0.80, Pillai's trace (V) at 0.1989, and effect size $f^2(V)$ at 0.2877, targeting isometric muscle strength across four independent groups. The analysis indicated a minimum required sample size of 48 participants, allocating 12 per group. To compensate for possible dropouts, the total sample was increased to 60 participants, with 15 individuals per group (**Wirth et al., 2016**) (figure 3).

[figure not shown]

Fig 3:sample size calculation using G power

Randomization, allocation concealment, and blinding

The enrolled participants will be randomized in a simple randomization way using (www.randomizer.org/links/) by another participant not involved in the data collection. Allocation concealment will be ascertained using sealed, opaque, sequentially numbered envelopes. The participants will be blinded to the assigned intervention group.

Participants

Sixty male football players from Al-Ahli and Al-Ittihad football clubs in the Kingdom of Saudi Arabia. Participants will be asked to sign a written informed consent that includes participation in the experimental trial, permission to use data and/or pictures, and informing them of their right to withdraw at any time (**Appendix I**).

Participants will be randomized into 4 equal groups: an experimental group (A, B, and C), and a Control group (D).

Experimental groups (A, B, and C)

Group A: Fifteen participants will receive mini-squat exercises at 30° knee flexion and leg press exercises

Group B: Fifteen participants will receive mini-squat exercises at 45° knee flexion and leg press exercises

Group C: Fifteen participants will receive mini-squat exercises at 60° and leg press exercises

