3. Mini-squat session will last 10 minutes. Squat will be performed in a slow and controlled manner (approximately 2 seconds down and 2 seconds up), with short rests of 15–30 seconds allowed every 1–2 minutes as needed. Approximately six minutes of active squatting will be completed per session, with the remaining time allocated for brief rests and transitions (**adapted from Hartmann et al., 2016**) (figure 9).

Fig 9: Mini squat exercise (adopted from Prentice, 2024).

Statistical analysis

All analyses were carried out using IBM SPSS Statistics version 27 (IBM Corp., Chicago, IL, USA).

- Subject characteristics will be analyzed using ANOVA, while the Chi-squared test will be used to compare the distribution of the affected side among the groups
- The Shapiro-Wilk test assessed the normality of the data, followed by Levene's test to verify the homogeneity of variances across groups.
- A mixed MANOVA will be conducted to evaluate the effects of group on the dependent variable(s).
- Post-hoc multiple comparisons were performed with Bonferroni correction to adjust for Type I error.
- Statistical significance was determined at a threshold of $p < 0.05$.

REFERENCES

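### Bonferroni post-hoc testing is valid but needlessly conservative: over the six group pairs Tukey or Holm holds the same 5% familywise limit with slightly more power

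*Combined protocol and SAP*

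**What the plan says.** All references are to the Combined protocol and SAP.

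- **Statistical analysis (Chapter III).** After a mixed MANOVA for the effect of group, "Post-hoc multiple comparisons were performed with Bonferroni correction to adjust for Type I error". On the level, "Statistical significance was determined at a threshold of" p < 0.05. The section names no set of comparisons and no divisor, and does not say whether the three outcomes share one correction.
- **Purposes of the study (Chapter I).** Each of the three purposes, one per outcome, opens "To investigate the difference between adding knee flexion mini-squat exercise at different angles" and lists 30°, 45° and 60°. The natural reading is angle against angle: A–B, A–C and B–C.
- **Hypotheses (Chapter I).** Each null hypothesis brings in the control as reference. The first concerns adding the three angles of "mini-squat exercises to leg press exercise and leg press exercise alone on quadriceps strength in football players". The natural reading is A–D, B–D and C–D, although each null can also be read as a single four-group hypothesis.
- **Sample size (Chapter III).** "An a priori power analysis was conducted for a repeated measures MANOVA with between-subject factors", with power "at 0.80, Pillai's trace (V) at 0.1989" and f²(V) "at 0.2877, targeting isometric muscle strength across four independent groups". The result is 48 players (12 per group), raised to 60 (15 per group) for dropout. No pairwise comparison is sized.

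**The concern.** The pairwise comparisons are what will tell the reader which angle, if any, adds something to leg press alone. The sample size is set for the omnibus test only, so these comparisons have whatever power is left at 12 to 15 players per arm. A procedure stricter than the 5% familywise limit requires therefore loses power where it is already short, and gets nothing beyond that limit in return. Purposes and hypotheses together make six pairs per outcome, and for six pairs there are standard procedures that keep the same limit and reject more often than Bonferroni.

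**Working it through.** **1. The plan's own figure.** With one response and 3 hypothesis degrees of freedom, f² = V/(1 − V) = 0.1989/0.8011 = 0.248. The noncentrality at N = 48 is 0.248 × 48 = 11.9, and an F test on 3 and 44 df then has power 0.800. So 48 is reproduced, but as the size for one four-group omnibus test. The stated f² of 0.2877 is not the value that this V implies (0.248); that discrepancy does not bear on the present point. Nothing in the calculation concerns a pairwise difference.

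**2. Inputs for the pairwise check.**
- From the documents: four equal groups, n = 15 per group, alpha 0.05.
- Assumed: two-sided tests; one outcome at a time with normal errors and a variance pooled over the four groups, so df = 4(n − 1) = 56; a standardised pairwise difference d from 0.5 to 1.5, since no effect or SD is given.

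**3. Critical values for six pairs at 15 per arm.**
- Bonferroni: 0.05/6 = 0.0083 per pair; t(1 − 0.05/12; 56) = 2.735.
- Tukey: q(0.95; 4, 56)/√2 = 2.648.
- Ratio: 2.648/2.735 = 0.968, so Tukey's simultaneous intervals are about 3% narrower.

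At 12 per arm (df 44) the values are 2.763 and 2.670.

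**4. Realised familywise error.** Simulating four equal means at 15 per arm, the chance of any false rejection among the six pairs is 0.040 with Bonferroni and 0.050 with Tukey.

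**5. Power per comparison.** Power = P(|T′| > c), where T′ is noncentral t on 56 df with noncentrality d√(n/2) = 2.739d.

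| Assumed d | Noncentrality | Bonferroni, 6 pairs | Tukey, 6 pairs | Gain (points) |
|---|---|---|---|---|
| 0.5 | 1.37 | 0.095 | 0.110 | 1.5 |
| 0.8 | 2.19 | 0.303 | 0.333 | 3.0 |
| 1.0 | 2.74 | 0.506 | 0.540 | 3.4 |
| 1.2 | 3.29 | 0.707 | 0.736 | 2.9 |
| 1.5 | 4.11 | 0.910 | 0.923 | 1.3 |

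The difference detectable with 80% power falls from d = 1.31 to 1.28. At 12 per arm and d = 1.0, power is 0.388 against 0.422.

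**6. Holm over the same six pairs.** Holm compares the ordered p-values with 0.05/6, 0.05/5, and so on up to 0.05. Its first step is Bonferroni's, so it rejects everything that Bonferroni rejects and sometimes more, and its chance of at least one rejection is identical. Simulated power for C against D at d = 1.0, where Bonferroni has about 0.506:
- only C differs from the rest: 0.535
- all three add-on arms differ equally from D: 0.533
- graded effects of 0.33, 0.67 and 1.0: 0.515

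The gain is therefore about 1 to 3 points, depending on the other means. In the first case the chance of at least one rejection is 0.747 with either procedure.

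**7. Dunnett for A, B and C against D.** The critical t is 2.414. At d = 1.2, power is 0.707 with Bonferroni over six pairs, 0.790 with Bonferroni over three, and 0.805 with Dunnett. Of the 9.8-point rise, 8.3 points come from cutting six comparisons to three and 1.5 from Dunnett itself. If the three angle pairs are then tested as a separate Holm family, the chance of any false rejection across the six pairs, with all means equal, is 0.081.

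**The case against.** The strongest reply is that nothing is broken. Bonferroni controls the familywise error, gives simple simultaneous intervals, and biases no estimate. The low power comes from 12 to 15 players per arm: at d = 0.8, changing from Bonferroni to Tukey moves power only from 30% to 33%. All of this stands, and it is why the point is one of efficiency only.

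A second reply is that six pairs is an inference. That is also right. The post-hoc sentence defines no family, so the figures for six pairs describe what the purposes and hypotheses imply together, not a rule that the plan states. If only the three comparisons with D were meant, Bonferroni would have power 0.608 at d = 1.0 against 0.628 for Dunnett, a loss of about 2 points. The argument for Holm does not depend on which family is meant.

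A reader might go further in two ways that the documents do not support:
- **That the angle-against-angle pairs waste error because the hypotheses do not name them.** They are study purposes, so error spent on them is spent on stated aims. Dunnett alone would leave those purposes untested.
- **That Dunnett buys about 10 points at the same error rate.** Most of that gain comes from the smaller family. With a second family for the angle pairs, the error over the same six comparisons rises to about 0.08, against 0.040 under Bonferroni and 0.050 under Tukey.

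**Conclusion.** The concern holds as a small efficiency point. For the six pairs that purposes and hypotheses jointly require, Bonferroni is valid but uses only about 0.040 of the 0.05 allowed. Tukey uses all of it and gains about 1 to 3 points of power per comparison over the assumed range d = 0.5 to 1.5 at 15 per arm. Holm gains a similar or smaller amount per comparison and nothing for the chance of at least one rejection.

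The power figures rest on the assumed d, two-sided tests and a single-outcome model with pooled variance, which simplifies the planned mixed MANOVA. Under that model Tukey's critical value is below Bonferroni's whatever d is, and Holm never rejects less than Bonferroni. Neither change makes up for a sample that was not sized for pairwise comparisons: at d = 1.0, 80% power needs 26 players per group with Bonferroni over six pairs and 25 with Tukey.

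**What to change.** Reword the post-hoc sentence in the Statistical analysis section so that it:

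1. names the six pairwise group comparisons per outcome as one family;
2. replaces Bonferroni by Tukey, which supplies simultaneous confidence intervals, or by Holm, which is valid for whatever family is declared;
3. says whether the correction is applied within each outcome or across quadriceps strength, hamstring strength and H:Q ratio. If each outcome is held at 0.05 separately, the error over three outcomes would be 1 − 0.95³ = 0.143 were they independent.

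Dunnett for A, B and C against D is an option only if those three contrasts are declared in advance as the sole confirmatory family, with the angle-against-angle comparisons labelled exploratory.

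The cost is a few sentences, with no extra players or measurements. Holm's matching confidence intervals are less simple than Bonferroni's; Tukey avoids that.
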